Q1 July-September 2025	
 a. Complete the final study protocol b. Submit the protocol & any other related documents for review to the Ethics Board/IRB. c. Receive Ethics Board/IRB protocol approval d. Participant recruitment
Q2 October-December 2025	
 a. Training and calibration of assessment tools b. Participant recruitment b. Baseline data collection c. Clean data d. Preliminary data analysis
Q3 January-March 2026	
 a. Continued data collection b. Follow up assessment c. Enter and clean data d. Data analysis e. Prepare manuscripts
Q4 April-June 2026	
 a. Data analysis b. Prepare manuscripts and the final report c. Present findings

	Year 1											
Activity	Q1			Q2			Q3			Q4		
Recruitment Screening and recruitment												
Data Collection Baseline and follow up data collection												
Data Analysis												
Draft and submit manuscripts												

Study Endpoints

The primary endpoint of this pilot study is to evaluate the effectiveness of different body composition measurement tools (aim 1) before and 6 months after metabolic surgery (MS), and the secondary endpoints are to study the aim 2 and 3.

Aim 1: Evaluate the Effectiveness of Different Body Composition Measurement Tools

Rationale: Traditional methods like BMI and waist circumference may not accurately reflect changes in body composition, especially in patients with severe obesity. Advanced tools can provide more precise data.

Approach:

Participants: Recruit patients with severe obesity (BMI \geq 40) scheduled for MS.

Body Composition Measurements: BMI, waist circumference, leg strength, skeletal muscle mass, fat mass, free fat mass, extracellular water (ECW) and total body water (TBW)

Measurement Tools: Use the Bioelectrical Impedance Analysis (BIA), 3-compartment (3C) model optical imaging, isotope dilution, densitometry (BOD POD), Dual energy X-ray Absorptiometry (DXA), and MRI scan

Data Collection: Measure body composition using traditional and advanced measurement tools at baseline (pre-surgery) and 6 months post-surgery.

Analysis: Compare the effectiveness of each tool in assessing body composition changes.

Expected Outcome: Advanced tools will provide more accurate and clinically relevant data compared to traditional methods. We will use DXA as the reference standard and compare other methods against it.

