Questionnaires (20 minutes): Participants will complete a questionnaire about their physical activity (attached) and diet (<https://asa24.nih.gov/>).

Participants will also complete 3 brief questionnaires that assess eating behaviors⁸⁻¹¹ (attached).

Abdomen, Pelvis and Thigh MRI scan (40 minutes): This scan will estimate the amount of skeletal muscle and regional (visceral) fat in the body. Participants will be required to remove all metal-containing objects from the body. Participants will be provided with earplugs and/or a headset to put over their ears for the duration of the scan. Participants will be given a call button if they need to notify the MRI tech during the scan. Participants will lie on their backs on the scanner table. The scan will start at the abdomen and proceed down to the thigh. The body will be scanned in sections. For the abdominal sections, participants will be asked to try their best to hold their breath a few times for approximately 15 seconds each time. Each participant will complete one scan.

Statistical Methods

Many of the comparisons will be exploratory and will need to be confirmed by follow-up studies. Continuous variables will be descriptively summarized by sample size, mean, standard deviation (SD), and standard error of the mean (SE). Type-II errors, i.e., failing to detect a significant effect when they exist, is important to this study. All tests of significance for comparisons will be performed at an alpha of 0.05. To address the goals outlined in the Aim, parametric statistical modeling, including analysis of covariance, multiple regression method and correlation analysis, will be employed where feasible. Paired testing will be used as well given the repeated measures design.

Data and Specimen Management

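### Aim 1 asks how accurate each tool is against DXA, but the methods the protocol names assess association or mean difference, not agreement

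*Protocol*

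**What the plan says.** Study Endpoints makes the evaluation of the measurement tools, before and 6 months after surgery, the primary endpoint. Under Aim 1 the analysis is one line: "Compare the effectiveness of each tool in assessing body composition changes". The reference is fixed: "We will use DXA as the reference standard and compare other methods against it". So is the conclusion sought: "Advanced tools will provide more accurate and clinically relevant data compared to traditional methods". The traditional methods in that contrast are BMI and waist circumference.

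Statistical Methods gives one short paragraph for all three aims. As the means of meeting the aims it says "parametric statistical modeling, including analysis of covariance, multiple regression method and correlation analysis, will be employed where feasible". It adds "Paired testing will be used as well given the repeated measures design" and "All tests of significance for comparisons will be performed at an alpha of 0.05". It also says that many comparisons are exploratory and need confirmation in later studies.

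The protocol defines neither accuracy nor effectiveness. It names no agreement statistic, error measure or acceptable difference from DXA.

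**The concern.** Aim 1 is a method-comparison question: how close does each tool come to DXA, and how much does that closeness vary between people? Correlation is unaffected by a constant offset or by a scale factor, so it cannot show that a tool reads too high or understates the loss. A paired test asks only whether the mean difference is zero. The more scattered the differences, the harder that is to reject, so a non-significant result is weak evidence of agreement and comes more easily to a poor tool.

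BMI (kg/m²) and waist circumference have no difference from DXA fat mass to compute. Under the named methods only association can be reported for them, and association does not establish that one tool is more accurate than another.

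At stake is the ordering of the tools, which is the main product of the pilot.

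**Working it through.** **Inputs from the protocol.** n = 20; alpha = 0.05 (two-sided assumed, as the protocol does not say). It gives no SD, margin or power figure, so there is no stated figure to reproduce.

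**Assumptions, not in the protocol.** True 6-month fat change: mean -25 kg, SD 8 kg, with SD 5 and 12 kg as a range. DXA is taken as error-free in steps 1 and 2, and with a 1.5 kg error SD in step 3. Simulated figures use 20,000 replicates.

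**1. A tool that understates change** (captures 75%, noise SD 2 kg).
- Mean error: 0.25 × 25 = 6.25 kg.
- Correlation with DXA: (0.75 × 8)/√((0.75 × 8)² + 2²) = 6/√40 = 0.95. At SD 5 it is 3.75/√18.06 = 0.88, and at SD 12 it is 9/√85 = 0.98.
- At n = 20 any r above 0.444 is significant.
- SD of the difference from DXA: √((0.25 × 8)² + 2²) = √8 = 2.83 kg. A paired test of this tool against DXA rejects in 100% of replicates. Correlation misses the error; a paired test against DXA would not.

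**2. A noisy tool with no mean bias** (error SD 6 kg).
- Limits of agreement: ±1.96 × 6 = ±11.8 kg.
- A paired test against DXA is non-significant in about 95% of replicates, as it must be when the true mean difference is zero.
- Correlation: 8/√(64 + 36) = 0.80 (simulated median 0.81), significant in more than 99% of replicates. Significant r together with a non-significant paired test: about 95%. The range is 85% at SD 5 and 95% at SD 12.

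**3. A precise tool with a small bias** (2 kg bias, error SD 1.5 kg in both tool and DXA).
- SD of differences: √(1.5² + 1.5²) = 2.12 kg. Limits of agreement: 2 ± 1.96 × 2.12, about -2.2 to +6.2 kg.
- Standardised bias 2/2.12 = 0.94. The paired test rejects in 98% of replicates.

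Read by p-value, tools 2 and 3 come out in the wrong order: the tool with limits of ±11.8 kg shows no difference and the one with limits of about -2 to +6 kg does.

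**4. How much bias a paired test can leave undetected.** An observed mean difference is non-significant up to t(19)/√20 = 2.093/4.472 = 0.47 SD of differences. Power of 80% needs a true bias of 0.66 SD. For a 6 kg SD these are 2.8 kg and 4.0 kg; for 2.12 kg they are 1.0 kg and 1.4 kg. The noisier the tool, the more bias it can hide.

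**5. Precision of the alternative.** Standard error of a limit of agreement: √(1/20 + 1.96²/38) = 0.389 SD. The 95% CI is ±2.093 × 0.389 = ±0.81 SD, or ±4.9 kg for a 6 kg SD.

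**The case against.** A reader might infer that the plan will declare a tool accurate on a significant r or a non-significant p. The protocol contains no such rule; it says only that effectiveness will be compared. The harm arises if results are read that way.

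A reader might also take the paired tests to be tool-versus-DXA tests. The sentence ties them to the repeated-measures design, and Aim 2 compares data before and after surgery, so pre/post testing is the more natural reading. Steps 2 to 4 then lose their paired-test content. Correlation, regression and analysis of covariance remain for Aim 1, and the bias problem in step 1 has one safeguard fewer.

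It would also be too strong to say that nothing on the list can detect a poor tool. Regression on DXA yields an intercept, slope and residual SD. For the 75% tool the slope differs significantly from 1 in about 96% of replicates. The residual SD is about 5.9 kg for the 6 kg-noise tool against 2.0 kg for an unbiased 2 kg-noise tool. Used that way, regression would answer part of the question, but the protocol does not say that it will be.

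Finally, the list is open (it is introduced as inclusive and conditional on feasibility), a separate analysis plan may add agreement statistics, and this is a pilot with largely exploratory comparisons. All of that stands, and it lowers the severity. It does not remove the mismatch between the methods chosen for the aims and the question that the primary aim asks.

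**Conclusion.** The point holds in a limited form. The primary question is accuracy against DXA, and the named methods, as stated, do not measure it. Correlation can sit near 0.95 with a mean error of about 6 kg. If tools are also tested against DXA in pairs, a tool with limits of ±11.8 kg escapes about 95% of the time while a precise tool with a 2 kg bias is flagged about 98% of the time. For BMI and waist the named methods offer only association.

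The kilogram figures rest on assumed values, but the direction holds across SDs of change from 5 to 12 kg. The documents do not support a claim that the trial will certify inaccurate tools, or that the named methods could never reveal them. This should be fixed before analysis; it does not invalidate the study.

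**What to change.** In Statistical Methods, name the Aim 1 analysis.

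- **Tools reporting the same quantity as DXA (fat mass, fat-free mass).** Give the mean difference from DXA with 95% CI, 95% limits of agreement with CIs, and a check for proportional bias (difference regressed on mean). Do this at each visit and for the 6-month change, without pooling the two visits as 40 independent pairs.
- **BMI and waist circumference.** Give cross-validated prediction error for DXA fat change, next to the same measure for each advanced tool, so that the traditional-versus-advanced contrast is made on one scale.
- **Interpretation.** Keep correlation as descriptive, and state that a non-significant paired test will not be read as accuracy.

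No new data are needed. The cost is protocol wording, a little more analysis, and visibly wide intervals: each limit of agreement carries about ±0.81 SD of differences at n = 20. That is a fair picture of what a pilot of this size can show.
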